Literature Review. Nonadherence to HIV treatment among people living with HIV in sub-Saharan Africa (SSA) is widespread, particularly young people. A meta-analysis found that 33% of all patients do not achieve $\geq 90\%$ antiretroviral therapy (ART) adherence (12). Moreover, an estimated one in four are lost to follow-up within a year of initiating ART(13). Young people (aged ~18-24) living with HIV (YPLH) have the highest risk for ART nonadherence (14) and treatment attrition when compared to older adults (2, 3, 14, 15) and younger adolescents and children (2, 14, 15). Consequently, YPLH's rate of virologic failure is also higher than other age groups (14), which leads to a greater risk for HIV transmission, AIDS-defining illnesses, and death.

YPLH in SSA face a host of developmental barriers to adherence. Youth strive for personal agency yet are subject to conflicting societal expectations, which, in many

African settings, involves the cultural value of social interdependence (16). Problems overcoming this transition delays adult role taking (17). Some YPLH have long relied on HIV care support from others and face an even harder transition to adult roles and responsibilities including treatment self-management. The poor adherence outcomes of youth who move from pediatric to adult HIV services evidences this claim (18). Moreover, the normative process of pursuing closer peer relationships while maintaining family support presents disclosure-related challenges (19) which affects seeking support for HIV care. Cognitive development is also factor in adherence. Neurobiological research reveals that self-regulation processes linked to healthy decision-making extends well into early adulthood (20). These developmental adherence barriers co-occur with individual and sociostructural contextual factors not unique to this population. HIV stigma is a major barrier (21) as is the cost and distance of travel to HIV clinics (22). Further, individuals with mental or behavioral health concerns are at risk for nonadherence (23, 24). YPLH are consequently left without adequate support networks and personal capabilities (e.g., self-efficacy) to manage their illness themselves, two of the strongest predictors of adherence in SSA (25). This includes support to help navigate contextual barriers to adherence.

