It is possible to play a Text-Based Adherence Game on low cost mobile phones without web access. Even with the advent of more technologically sophisticated games, text-based games continue to be immensely popular as smartphone apps (38). A text-based game facilitated by a fully automated computer system and played solely through text messages is a possible. This strategy has not been previously tested. Game components could consist of ART and clinic visit reminders; patient and clinic monitoring of ART adherence, clinic attendance, viral load, and CD4+ count; personalization of settings; questions, polls, and messages related to ART adherence and retention in care problems; goals, point reinforcers, achievements, and game levels; peer competition; facilitated social support interactions; linkage to HIV clinic counselors and medical staff; optional use of a progress monitoring website; and an engaging storyline. A Text-Based Adherence Game also offers an advantage over digitally complex adherence games by being easily modified. This is an important consideration as a game’s relevance can diminish over time, and new barriers to adherence may emerge which need to be quickly addressed.

Modified Social Action Theory(9) (Figure 2) can guide the creation of a Text-Based Adherence Game. The model has rarely been applied to HIV medical adherence(39) yet experts advocate for its use in SSA settings for this purpose(40). It differs from more

[figure not shown]

Figure 2. Modified Social Action Theory

individualistic theories with its emphasis on contextual factors and social interdependence. The construct of social interdependence in our model is defined as the relationship and interaction between YPLH and a person in their life who provides support for adherence. Adherence behaviors will alter this relationship. For example, a friend of an HIV patient who reminds the patient to take her HIV medication could

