cognitive or medical limitations per clinician report, (5) possess a cellphone, and (6) able to give consent. *Adolescents living with HIV (ALH) between the ages 12-17 will also be eligible to participate in focus groups and cognitive interviews as part of a separate component of the Development Phase. Their eligibility criteria is as follows:* (1) *read English and speak English or a local language spoken by clinic staff (e.g., Twi),* (2) *in medical care for HIV and receiving ART at our clinic,* (3) *aware of their HIV status as per parent/guardian report,* (4) *not impaired by cognitive or medical limitations per clinician report,* (6) *able to give assent, and* (7) *their parent/guardian is able to give consent. Parents or guardians of ALH are also able to participate in focus groups and cognitive interviews as part of this separate component. Parent eligibility is as follows:* (1) *speak English or a local language spoken by clinic staff (e.g., Twi),* (2) *own a mobile phone,* (3) *aware of their child's HIV status,* (4) *not impaired by cognitive or medical limitations per clinician report, and* (6) *able to give consent.* Participants in the randomized pilot must have also demonstrated a recent detectable viral load. Study staff will NOT make changes to ART regimens and participants will be encouraged to speak with their doctor if they have concerns about their medications or side effects of these medications. Any unexpected ethical issues that arise with our participants will be discussed immediately with the PI. All participants will receive a resource packet including information on ART as well as references to local health and social services. We will also encourage participants to identify a treatment monitor to take part in the game. This will not be a requirement for our study, however, because those who begin playing the game without a monitor will be incentivized via game rewards to recruit one (and we will assess this occurrence). Participants without a monitor will be assigned a peer educator to fill this role. Inclusion criteria for treatment monitors includes: 1) *read English and speak English or a local language spoken by clinic staff,* (2) *target HIV patient has agreed to their participation,* (3) *aware of target patient's HIV status as per patient report,* (5) *possess a cellphone, and* (6) *able to give consent.*

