on Centers for Disease Control and Prevention guidelines (44) led by a bachelors-level clinic counselor, as needed contact with counselors, and access to a clinic social event held once per year. They will then be shown the game by a trained RA. The basic elements of the game will be demonstrated and YPLH will have an opportunity to interact with the system, with study staff, to build interest and understanding. Participants will be asked permission to enroll a treatment buddy to participate in the game as well. This person will be consented by study staff. The game also pairs participants with a peer educator who has shown good medical adherence by clinic report and is trained to provide phone peer support. Three iterations of increasing game length (two, four, and eight weeks) and number of participants ($n = 6, 8$, and 10) will test game prototypes. After each iteration participants will be assessed with a semi-structured cognitive interview (45) to gauge participants' opinions of the game, and its clinical utility, relevance, strengths and weaknesses, ease of use, and ability to capture their experiences (See Appendix 1 for interview guide). Audio from cognitive interviews will be digitally recorded and transcribed. They will also complete quantitative measures for similar feedback. In addition, participants will be assessed before and after the third iteration on main study variables to explore shifts in our primary and secondary outcomes. Information gained after each iteration will be used by research staff to alter the game. Study staff will also contact participants after they enroll via a phone call to trouble shoot problems playing the game. YPLH will be remunerated with an allowance of 40 Cedis for each assessment. They will also be given 40 Cedis worth of prepaid phone credits to send text messages. Treatment monitors will be compensated 40 Cedis.

[figure not shown]

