Hypothesis One (Aim 1). The Text-Based Adherence Game will be feasible, appealing, and useful. YPLH in the third open trial iteration of the Text-Based Adherence Game will show shifts in primary and secondary outcomes in the expected directions from pre-post assessments.

Hypothesis Two (Aim 2). Compared to participants in the control group, participants in the Text-Based Adherence Game will show at 6 and 12 months post-intervention: improved ART adherence, clinic attendance, biologic functioning (lower

Figure 5. Assessment Schedule

HIV viral load, higher CD4 count), and shifts in secondary outcomes (social support, self-efficacy, etc.) consistent with adherence promotion. Repeated measures ANCOVAs will be used to test differences over time between study conditions on each outcome variable. Missing data will be handled using multiple imputation. Potential imbalance between treatment conditions on baseline characteristics will be addressed using inverse probability of treatment weights (51). Power: As this is a pilot study and the impact of the intervention is not known, there may not be adequate power to determine its efficacy; also, pilot studies are not designed to provide accurate estimates of effect sizes upon which to base large trials(52). However, the small pilot may provide a “signal” of impact on its primary outcomes and we will examine the effects of the intervention on secondary outcomes based on Social Action Theory. We assume that retention over one year is at least 86% based on past studies conducted in Ghana (31, 53) thus 52 cases of the 60 enrolled in the pilot are available for analysis. Power analyses were run with G*Power 3(54). The model assumed 3 assessments with 52 individuals. The analyses with alpha of 0.05 and power 0.80 will be able to detect small to medium effects.

DISSEMINATION OF RESULTS

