6. “There are people in my life that are supportive about avoiding alcohol use” _____

Modified Social Provisions Scale

Instructions

The next set of questions are about a particular person who you rely on the most for helping you with your HIV treatment on a daily basis. This person is typically a friend, parent or other family member, or your treatment supporter (also known as a treatment buddy) but they can also be a peer educator, clinic counselor, or someone else. He or she may remind you to take your medication, make sure you get to your HIV clinic appointments, or help you in other ways. Please identify this person:

- 1- Treatment supporter (treatment buddy)
- 2- Same-age or younger friend
- 3- Older adult friend
- 4- Parent
- 5- Other family member (Please describe your relationship to this person: _____)
- 6- Peer educator
- 7- Clinic counselor
- 8- Someone else (Please describe your relationship to this person: _____)

I'm going to ask you about your relationship with this person. Please tell me how much each statement describes your situation by using these responses. So, for example, if you feel a statement is VERY TRUE you would say Strongly Agree. If you feel a statement CLEARLY does not describe your relationship, you would answer Strongly Disagree?"

Strongly Disagree = 1

Agree = 3

Disagree = 2

Strongly Agree = 4

1. This person will help me if I really need it.
2. I do not have a close relationships with my this person.
3. I can't turn to this person in times of stress.
4. This person calls on me to help him/her.
5. This person likes the same social activities I do.
6. This person does not think I am good at what I do.
7. I feel responsible for taking care of this person.
8. This person thinks the same way I do about things.
9. I do not think that this person respects what I do.
10. If something went wrong, this person would help me.
11. I have a close relationship with this person that make me feel good.
12. I can talk to this person about decisions in my life.
13. This person values my skills and abilities.
14. This person does not have the same interests and concerns as me.
15. This person does not need me to help take care of them.
16. This person is a trustworthy person I can turn to if I have problems.
17. I feel a strong emotional tie with this person.
18. I cannot count on this person for help if I really need it.
19. I do not feel comfortable talking about problems with this person.

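### The Modified Social Provisions Scale cannot record a respondent who relies on nobody, and at follow-up that state may be more common among controls

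*Combined protocol and SAP*

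**What the plan says.** The Modified Social Provisions Scale (Appendix 3) opens by asking the respondent to identify the "particular person who you rely on the most for helping you with your HIV treatment on a daily basis". The choice is wide: the person is typically a friend, relative or treatment supporter, "but they can also be a peer educator, clinic counselor, or someone else". The last of the eight codes is "8- Someone else (Please describe your relationship to this person". No code means nobody, and there is no skip or scoring rule for that case. All 24 items, each answered 1 to 4, describe the named person.

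The arms differ in access to such a person. Under Inclusion criteria, the protocol says of the game's monitor role: "Participants without a monitor will be assigned a peer educator to fill this role". The open-trial procedures, which the pilot reuses subject to open-trial feedback, add: "The game also pairs participants with a peer educator". Controls receive standard of care, which includes one adherence counselling session and counsellor contact as needed.

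The Literature Review defines social interdependence as the relationship with "a person in their life who provides support for adherence". On missing values the Data Analytic Plan says only: "Missing data will be handled using multiple imputation". It gives no imputation model and no rule for individual scales.

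**The concern.** The protocol's own rationale makes respondents without support foreseeable: "YPLH are consequently left without adequate support networks". Someone who relies on nobody has two ways through this scale. They can name a person they do not really rely on, which hides their state, or they can leave all 24 items blank.

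A blank here is not an unobserved score, because there is no relationship to rate. If it is imputed from people who do have a supporter, the unsupported respondent is given a supported person's score. After baseline the game arm has a peer educator to name and the control arm is not given one, so this can happen at different rates in the two arms at 6 and 12 months. Baseline comes before the game, so there it can affect both arms alike.

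At stake is one pathway of the trial's theory, the relationship with a supportive person. Part of what the game may do is supply such a person, and this scale as written could miss that part.

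**Working it through.** **The plan's own figures.** Retention of 86% gives 60 × 0.86 = 51.6, rounded to the stated 52. With 52 people, three assessments, alpha 0.05, power 0.80 and sphericity, the detectable group-by-time effect is f = 0.211, 0.178 and 0.138 at assumed correlations of 0.3, 0.5 and 0.7. That lies between conventional small (0.10) and medium (0.25), as stated. The power statement does not depend on this point. Allocation is not stated; I assume 1:1, so 26 per arm.

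**Assumed inputs, none of them in the documents.**
- p, the share with nobody at all: 5-30%.
- g, how far such people sit below those with a usual supporter: 1-2 SD.
- h, how far an assigned peer educator rates below a usual supporter: 0 or 0.5 SD.

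The calculation also takes the extreme path: every unsupported control leaves the scale blank, and every unsupported game participant rates the peer educator. If some unsupported controls name a nominal person and score low, the loss shrinks in proportion.

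**Step 1, people affected.** 26 × 0.05 = 1.3 to 26 × 0.30 = 7.8, so about 1 to 8 controls.

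**Step 2, gain from supplying a supporter if the state is recorded and scored low (h = 0).** Difference = p × g. Lowest: 0.05 × 1 = 0.05 SD. Middle: 0.20 × 1.5 = 0.30 SD. Highest: 0.30 × 2 = 0.60 SD.

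**Step 3, the same gain as analysed.** Imputing from supported controls raises the control mean by p × g, so the difference is p × g − p × g = 0. Dropping the blanks gives the same expected mean.

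**Step 4, when the sign changes.** Recorded: p × (g − h). Analysed: −p × h. With h = 0.5:

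| p | recorded, g = 1.5 | recorded, g = 2 | analysed |
|---|---|---|---|
| 0.10 | 0.10 | 0.15 | −0.05 |
| 0.20 | 0.20 | 0.30 | −0.10 |
| 0.30 | 0.30 | 0.45 | −0.15 |

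With h = 0 the analysed value is 0 throughout. The negative sign comes from h alone.

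**Step 5, with a further gain.** Suppose the game arm also sits 0.5 SD above supported controls, with p = 0.20 and g = 1.5. Recorded: 0.5 + 0.20 × 1.5 = 0.80 SD. With blanks dropped: 0.50 SD. In 4,000 simulated trials of 26 per arm, compared by a two-sample t test at one visit, power was 74% and 37%. The 0.5 SD gain is kept; only the 0.30 is lost.

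**Step 6, why a floor score should not be the main remedy.** The scale runs from 24 × 1 = 24 to 24 × 4 = 96. Take assumed means of 65 for an assigned peer educator and 40 for no one, with p = 10-30%. The gain is p × (65 − 40) = 2.5 to 7.5 points. Scoring no one at 24 gives p × (65 − 24) = 4.1 to 12.3 points, which is 41/25 = 1.64 times as large, in the game's favour.

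**The case against.** The strongest reply is that few people will be unable to answer. A reader might infer that anyone without a treatment supporter or monitor is shut out. The text does not support that: the treatment buddy is only code 1, and the other codes admit friends, parents, other relatives, a peer educator, a clinic counsellor or anyone else. Controls have counsellor contact under standard of care, and the adolescent focus group guide says that patients are asked to have a treatment monitor. The gap is confined to people who rely on nobody at all, and the documents do not show how many there are.

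The questionnaire is read by computer with staff present, so some unsupported respondents will name a nominal person and be scored. Equally, being assigned a peer educator does not make that educator the person most relied on each day. A richer imputation model that used the other support scales could also pull imputed values down. These points limit the size of the effect. They do not give the scale a way to record the state.

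A reader might also infer that Hypothesis Two's social support comparison rests on this scale. It does not. The MOS Social Support Survey and the Adherence and Risk Reduction Social Support items can both be answered by someone with no support, so a gain could still show there. Figure 5, which describes the secondary outcomes, is not shown, so this scale's status is inferred from the social interdependence construct; it is not among the listed primary outcomes.

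Finally, the Measures section allows instruments to be revised after formative work. That leaves room for the change but does not make it.

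**Conclusion.** The point holds in a narrow form and is a cheap improvement. The instrument cannot record a respondent who relies on nobody, and the design may make that state more common among controls at 6 and 12 months. Imputing the resulting blanks from people with supporters would remove the part of any gain on this scale that comes from supplying a supporter. Under the assumed p of 5-30% and g of 1-2 SD, and with every unsupported control leaving the scale blank, that part is 0.05 to 0.60 SD. The true share is unknown.

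A reader might go further and conclude that the game could appear to reduce support. That requires assigned peer educators to rate below usual supporters, and nothing in the documents says so; if they rate equally, this part of the effect is zero, not negative. Nor does the whole effect vanish unless all of it comes from supplying a supporter.

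**What to change.** - Add a ninth code, 'No one', that skips the 24 items. The disclosure question within the HIV Treatment Readiness Measure in the same questionnaire already offers such an answer.
- Report having any supporter (yes/no), and who was named, by arm at baseline, 6 and 12 months.
- State in the Data Analytic Plan that 'No one' is an observed answer and is not imputed as missing at random.
- Present the scale among those who named a person as a conditional analysis, noting that this group is formed after randomisation and may differ by arm.
- Use a low score for 'No one' only as a sensitivity analysis over a prespecified range of values, not as a single floor score.

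The cost is one response code, one skip and a few sentences in the analysis plan. The downside is small: fewer scale scores in the conditional analysis.
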